2.3 BENEFIT/RISK ASSESSMENT

Most patients with mutations/rearrangements that confer hyperactivation of the RAS-MAPK pathway have a poor prognosis. The combination of SHP2 inhibition together with anti-PD1 inhibition provides a potentially novel targeted treatment for these patients with advanced solid

tumors harboring mutations resulting in hyperactivation of the RAS-MAPK pathway. RAS family oncogenes are frequently activated by mutations in human cancers and KRAS G12C is the predominant mutation in NSCLC (39). Therapies specifically targeting the mutant KRAS G12C, shown to be clinically effective in these previously intractable cancers. Mechanism of action and preclinical data suggest that the anticancer activity of KRAS G12C inhibitors deepened when combined with SHP2 inhibition.

SAR442720 is currently being administered to humans in a Phase 1 dose-escalation and dose-expansion monotherapy study, Protocol RMC 4630 01, (<https://clinicaltrials.gov; NCT03634982>) evaluating its safety, tolerability, preliminary efficacy, MTD, and RP2D, PK, and PD profiles. More detailed information about the expected benefits and risks and reasonably expected AEs of SAR442720 based on clinical and pre-clinical data and class of drugs may be found in the SAR442720 Investigator's Brochure (IB).

Pembrolizumab is a PD-1-blocking antibody indicated for several indications including melanoma, NSCLC, Head and Neck Squamous Cell Cancer (HNSCC), Classical Hodgkin Lymphoma (cHL), Primary Mediastinal Large B-Cell Lymphoma (PMBCL), Urothelial Carcinoma, Microsatellite Instability-High Cancer, Gastric Cancer, Cervical Cancer, Hepatocellular Carcinoma (HCC), Merkel Cell Carcinoma (MCC), Renal Cell Carcinoma (RCC). Pembrolizumab has been administered in clinical trials as a single-agent and in combination with a variety of compounds and therapies. Further information can be found in the current version of the pembrolizumab US package insert.

The Phase 2 part of the adagrasib clinical study 849-001 is evaluating the clinical activity of MRTX849 in cohorts of patients who have tumors with the KRAS G12C mutation. As of 30 August 2020, clinical activity data have been reported for patients with NSCLC administered MRTX849 at the Phase 2 dose of 600 mg BID in Phase 1/1b or Phase 2 cohorts.

2.3.1 Risk assessment

2.3.1.1 Potential risks of SAR442720

Given the limited clinical experience to date, the potential risks are based on the combinations of emerging clinical safety data, pre-clinical data and class effects. Until the cut-off date of the most recent IB (17-July-2021), cumulatively 242 participants have been exposed to the drug, 113 participants in the monotherapy trial (RMC 4630-01), 112 participants in the RMC 4630-02 (cobimetinib and osimertinib combination study) and 17 participants in the pembrolizumab study (TCD16210). Based on the emerging safety data in the aforementioned studies, especially data coming from the monotherapy trial, the following potential risks have been identified: edema, diarrhea, anemia and thrombocytopenia, which are summarized in [Table 11](#).

Most AEs observed in RMC-4630-01, RMC-4630-02, and TCD16210 are low grade in severity, primarily Grade 1 or 2, and are managed adequately in the clinic.

The safety and tolerability profiles of SAR442720 were consistent with the mechanism of action and RAS pathway inhibition. Frequently reported treatment-emergent AEs of any grade regardless of relationship to study drug by PT or group of clinically associated PTs included edema includes hemodynamic edema, effusions, and fluid overload events (48.7%), diarrhea (48.7%), anemia and fatigue, and thrombocytopenia (32.7% each), dyspnea (31.9%), nausea (21.2%), and aspartate aminotransferase increase (20.4%). Grade ≥ 3 TEAEs by PT or group of clinically associated PTs included anemia (16.8%), thrombocytopenia (15.0%), dyspnea (12.4%), edema (9.7%), and pneumonia (6.7%). The most frequently reported treatment-related AEs, as assessed by the Investigator, of any grade, by PT or group of clinically associated PTs were diarrhea (35.4%), thrombocytopenia (30.1%), edema (28.3%), fatigue (28.3%), and anemia (27.4%). Grade ≥ 3 related AEs reported included thrombocytopenia (13.3%), anemia (11.5%), hypertension and diarrhea (4.4% each). Data on the intermittent schedule suggest that it may be better tolerated than the daily schedule. For further detailed safety profile and incidence of TEAEs please refer to the most recent IB.

Potential risks of SAR442720 have been determined based on the emerging clinical safety data and are listed in [Table 11](#). Amongst the potential risks associated with SAR442720, diarrhea is managed using Imodium and Lomotil in the majority of participants, thrombocytopenia is primarily managed with dose interruptions, Grade 3 anemia is managed with blood transfusions with or without dose interruptions, and edema is managed with diuretics such as Lasix or spironolactone.

Table 11 - Potential risks of SAR442720

[figure not shown]
Potential Risk	Descriptions and Guidance for the Investigator
Edema*	
Edema of any grade was reported in 48.7% (55/113) of participants in study RMC-4630-01. Grade ≥3 edema was reported in 11 participants (9.7%) in study RMC-4630-01. The median time to first onset of edema was 17 days, with a median duration of 14.5 days for the resolved events.
 
Guidance to the Investigators:
 
Observe for early signs of edema and investigate for potential other clinical causes including medications. Follow institutional guidelines to manage edema including cessation of other medications known to be associated with the development of edema, if clinically indicated. Follow protocol dose modification guidelines in the event of observing edema.

Thrombocytopenia*	
Thrombocytopenia AEs, of any grade, were reported in all dosing cohorts, including RP2DS of 200 mg (D1D2) in RMC-4630-01 study. The overall incidence was 33% (37/113) including 15.0% (17/113) Grade 3-4 events. No Grade 3-4 bleeding events in conjunction with thrombocytopenia have been reported as of data cutoff date. Median time to onset of thrombocytopenia** was 15 days from the start of study treatment and median duration was 24.0 days.
 
Guidance to the Investigators:
 
These recommendations refer only to the management of uncomplicated thrombocytopenia, ie, decrease in platelet counts without any accompanying clinical events of bleeding/significant bruising or other known risk factors for bleeding.
 
For Grade 1-2 events (platelet level 50 000 to <100 000 [entry criteria]), continue treatment at current dose level and frequency and monitor closely.
 
For Grade 3-4 events (platelet level <50 000), manage per institutional guidelines and interrupt dosing until patient recovers to Grade 1 or better (platelet level >75 000). If recovery occurs, the Investigator may resume dosing at the same dose level and frequency, if clinically appropriate. If Grade 3-4 events recur, hold dose until recovery to Grade 1 or better and consider re-introducing study drug at reduced frequency, or withdrawing patient from study therapy.
 
For thrombocytopenia associated bleeding event or in participants with significant additional risk factors for bleeding, the general dose modification guidelines should be considered. The Investigator may interrupt or discontinue study treatment as deemed medically appropriate.

Diarrhea	
Diarrhea AEs, of any grade, were reported in 48.7% (55/113) participants in the RMC-4630-01 study. Grade ≥3 AEs were reported in 5.3% (6/113) participants. Median time to onset of diarrhea was 9.0 days from the start of study treatment and median duration was 4.0 days.
 
Guidance to the Investigators:
 
Evaluate for other or concomitant causes, including medications (eg, stool softeners, laxatives, antacids), infection including Clostridium difficile, malabsorption/lactose intolerance, fecal impaction, and dietary supplements high in fiber.
 
For Grade 1 or 2 diarrhea, dietary modifications should be considered including cessation of lactose-containing products, eats small meals, and adequate hydration. Consumption of the BRAT (banana, rice, apples, toast) diet may be helpful. In addition, loperamide or codeine may be used or alternatives in refractory cases such as octreotide and budesonide.
 
For >Grade 2 diarrhea, consider hospitalization for fluid and electrolyte replacement and antibiotics, particularly if accompanied by fever or Grade 3-4 neutropenia.
 
Consultation with a gastroenterologist should be considered, particularly for severe or refractory events.

Anemia*	
Anemia AEs of any grade were reported in 37.2% (42/113) participants in the RMC-4630-01 study. Grade ≥3 AEs were reported in 16.8% (19/113) participants. Median time for onset of anemia*** was 21.5 days and median duration was 21.5 days.
 
Guidance to the Investigators:
 
Monitor closely and provide supportive care according to institutional standards. Interrupt study treatment as clinically appropriate. Dose interruption or discontinuation may not be required depending on baseline hemoglobin and transfusion history.

* Includes edema peripheral, pleural effusion, periorbital edema, face edema, pericardial effusion, localized edema, peripheral swelling, ascites, generalized edema, eyelid edema, fluid retention, joint swelling, lip edema, and pulmonary edema; thrombocytopenia includes thrombocytopenia and platelet count decreased, anemia includes anemia, anemia macrocytic, hemoglobin decreased, and normocytic anemia

** Time to and duration of thrombocytopenia was calculated using laboratory data.

*** Time to and duration of anemia was calculated using laboratory data.

Thromboembolic events:

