E 22. Medication and supplements that may interfere or potentiate with SAR442720 and/or adagrasib metabolism or toxicity PRIOR or DURING study intervention are excluded:

- Strong CYP3A4 inducers or inhibitors (within 7 days prior)
- Strong P-glycoprotein (P-gp) inhibitors (eg, cyclosporine, tacrolimus; within 7 days prior)
- Strong Breast Cancer Resistance Protein (BCRP) inhibitors (eg, eltrombopag; within 7 days prior) (applies to Part-3 only)
- Proton pump inhibitors (within 3 days prior) or H2-receptor antagonists (within 1 day prior) during the dose escalation portion of the study
- Medications known to prolong QTc interval
- Acetylsalicylic acid (low dose aspirin, anticoagulation with low-molecular weight heparin or direct Factor X inhibitors and LMWH are allowed. Prophylactic LMWH is also allowed for high risk patients with hypercoagulability).

Diagnostic assessments

E 23. Inadequate organ and bone marrow function at the Screening visit:

- Absolute neutrophil count (ANC) $<1000 \mu\text{L} (1 \times 10^9/\text{L})$.
- Platelets $<100 \times 10^3 \mu\text{L}$ (after at least 3 days without platelet transfusion).
- Hemoglobin $<9 \text{ g/dL}$ or $<5.6 \text{ mmol/L}$ (without transfusions within 2 weeks of initiation of IMP).
- Total bilirubin $>2 \times \text{ULN}$.
- AST and/or ALT $>3 \times \text{ULN}$ (or $>5 \times \text{ULN}$ for participants with liver metastases).
- Blood creatinine $>1.5 \times \text{ULN}$ or creatinine clearance of $<50 \text{ mL/min}$ (using Cockcroft Gault formula or 24-hour urine collection)
- Prothrombin time (PT)/international normalized ratio (INR) and activated partial thromboplastin time or partial thromboplastin time (aPTT/PTT) $>1.3 \times \text{ULN}$ or outside the therapeutic range of the local laboratory if receiving therapeutic anticoagulation that would affect the PT/INR.

Other exclusions

E 24. Individuals accommodated in an institution because of regulatory or legal order; prisoners or participants who are legally institutionalized.

E 25. Participant not suitable for participation, whatever the reason, as judged by the Investigator, including medical or clinical conditions, or participants potentially at risk of noncompliance to study procedures.

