10.9 APPENDIX 9: GENERAL GUIDELINES FOR THE MANAGEMENT OF ADVERSE EVENTS

Investigators must be extremely vigilant and be ready to intervene early in the management of AEs, particularly immune-related AEs because the onset of symptoms of irAEs (eg, pneumonitis) may be subtle.

- Detailed guidance for the management of specific AEs (colitis, endocrine AE, pneumonitis, renal AE, dermatologic AE, hepatitis, ophthalmologic AE [uveitis], etc.) is provided in [Table 27](#).
- General guidance is provided in [Table 26](#) below.
- If a participant experiences several AEs which involve different recommendations, the most conservative recommendation should be followed.

The recommendations provided in [Table 26](#) and [Table 27](#) should be seen as guidelines, and the treating physician should exercise clinical judgment based on the symptoms and condition of the individual participant.

Table 26 - General guidelines

Severity	Withhold/restart /discontinue SAR442720 treatment	Withhold/restart/discontinue the combination drug (Pembrolizumab or adagrasib) treatment	Supportive care
Grade 1	No action	No action	Provide symptomatic treatment.
Grade 2	No action	May delay or omit the pembrolizumab dose until Grade ≤ 1 Adagrasib dose modification/ dose interruption per Investigators discretion unless otherwise defined in Table 27 .	Consider systemic corticosteroids (Prednisone 0.5 to 1 mg/kg/day or equivalent) in addition to appropriate symptomatic treatment.
Grade 3	Delay the treatment until toxicity improves to Grade ≤ 1 or baseline.		For any Grade 3-4 immune-related adverse event, if symptoms worsen or do not improve on adequate corticosteroids (prednisone 1 to 2 mg/kg/day or equivalent) within 48 to 72 hours), consider additional immunosuppressive agents (to be selected from agents such as: infliximab, cyclophosphamide, cyclosporine and mycophenolate mofetil). Referral of the participant to a specialized unit for assessment and treatment should be considered.
Grade 4	Permanently discontinue		

Table 27 - Dose modification guidelines for combination regimens (SAR442720 and pembrolizumab combination or SAR442720 and adagrasib combination)

AE	Action

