Hematologic lab abnormalities > Grade 3	
Assess for other causes. Hold concomitant medications associated with myelosuppression.
 
Grade 3 neutropenia, thrombocytopenia: Hold both drugs if clinically indicated until $<$ Grade 1 or baseline. If improves within 4 weeks, restart pembrolizumab or adagrasib at same dose and administer SAR442720 one dose level lower. If does not improve within 4 weeks, discontinue both drugs.
 
Grade 3 febrile neutropenia: Hold both drugs until fever resolves and ANC $<$ Grade 1 or baseline. If improves within 2 weeks, restart pembrolizumab at same dose and SAR442720 and adagrasib 1 dose level lower. If does not improve within 2 weeks, discontinue both drugs.
 
Grade 3 anemia: Assess transfusion history. Transfuse per institutional guidelines. Continue pembrolizumab, and hold SAR442720 if clinically indicated until $<$ Grade 1. If improves within 4 weeks, restart SAR442720 one dose level lower. If does not improve within 4 weeks, consider discontinuation of both drugs. Hold adagrasib until \leq Grade 1 or baseline and may resume at the same dose level.
 
Grade 4 cytopenias: Hold both drugs until resolves to $<$ Grade 1 or baseline. If improves within 4 weeks, restart both drugs; reduce both SAR442720 and adagrasib one dose level lower (pembrolizumab dose reduction is not allowed). If does not improve within 4 weeks, discontinue both drugs.
 
Thrombocytopenia associated with clinically significant bleeding, at any level: Hold both drugs and follow hemorrhage recommendations.
 
Uncomplicated Thrombocytopenia (without clinically significant bleeding):
 
Grade 1 to 2: Continue treatment at current dose level and frequency and monitor closely
 
Grade 3 to 4: Manage per institution guidelines and interrupt dosing of both study drugs until participant recovers to Grade 1 or better. If recovery occurs, the investigator may resume dosing both study drugs at the same dose level and frequency, if clinically appropriate. If Grade 3 to 4 events recur again, hold dose until recovery to Grade 1 or better and consider re-introducing study drug at reduced frequency, or withdrawing participant from study therapy.
 
Please contact Medical Monitor for ambiguous cases.

AE	Action

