Section 2.3.1 Risk assessment	The following statement was removed: “Phototoxicity studies with SAR442720 have not been completed. Therefore, participants taking SAR442720 should use appropriate protection when exposed to UV radiation”	In vitro and in vivo studies have been conducted and no indication of phototoxicity was observed. This information is included in the SAR442720 Investigator’s Brochure (IB) v3.
	The following text, “approximately 6.4x of unbound C _{max} ”, was adjusted to “approximately 17x of unbound C _{max} ”.	Clarification.
	The following paragraph was added: “Emerging data from ongoing studies identifies anemia as a new potential risk based on clinical data and preclinical evidence. In the monotherapy study (n=82), anemia AEs (Standardized MedDRA Query [SMQ]), of any grade, were reported in 26 (31.7%) participants, including 11 (13.4%) participants who required blood transfusions. Grade 3 anemia events were reported in 13 (15.9%) participants; 3 SAE including 1 event related to study drug. No Grade 4 anemia events have been reported to date. Median time to onset of anemia was 22 days from the start of study treatment, and median time to recovery was 21 days. In addition, 54 (65.9%) participants had a hemoglobin grade shift from baseline, of which 27 participants were anemic at baseline, among which 3 (3.7%) participants had a hemoglobin shift from Grade 1 to Grade 3 and 5 (6.1%) participants had a hemoglobin shift from Grade 2 to Grade 3. The other 27 participants were normal at baseline, among which 6 (7.3%) participants had a Grade 2 worsening and 2 (2.4%) participants had a Grade 3 worsening.”	Anemia is the third risk which has been identified as potential risk. It was added to the protocol as to alert the investigators.

Section # and Name	Description of Change	Brief Rationale

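### After Grade 3 anemia, Table 27 releases SAR442720 only below Grade 1 and omits return to baseline, unlike Table 26 and the related Table 27 rules

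*Protocol*

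**What the plan says.** **Protocol, Appendix 9, Table 27, Grade 3 anemia.** After assessing transfusion history and transfusing by local practice, the investigator is told: "Continue pembrolizumab, and hold SAR442720 if clinically indicated until" the anemia is below Grade 1. No alternative of return to baseline is given for SAR442720. The entry goes on: "If improves within 4 weeks, restart SAR442720 one dose level lower". And: "If does not improve within 4 weeks, consider discontinuation of both drugs". Its last sentence, on adagrasib, lets that drug resume at the same dose level once the anemia is at Grade 1 or lower, or at baseline.

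**Protocol, Appendix 9, Table 26, Grade 3 row, SAR442720.** "Delay the treatment until toxicity improves to Grade" 1 or lower, or to baseline. The introduction to the appendix describes Table 26 as general guidance and Table 27 as detailed guidance for specific events. It also says that both are guidelines to be applied with clinical judgment.

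**Protocol, Section 2.3.1.1, Table 11, Anemia.** "Dose interruption or discontinuation may not be required depending on baseline hemoglobin and transfusion history". No restart threshold is stated there.

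**Protocol, Section 5.2, E 23.** Only hemoglobin below 9 g/dL (5.6 mmol/L) excludes, with the entry value taken "without transfusions within 2 weeks of initiation of IMP". Participants with anemia milder than that may enter.

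**The concern.** For the same drug and the same grade, Tables 26 and 27 differ in two ways: the grade cut (1 or lower against below 1) and whether baseline counts. The anemia entry also differs within itself. In Part-3, a participant back at the entry hemoglobin may resume adagrasib under one sentence while SAR442720 stays on hold under another. If Grade 4 anemia is managed as a Grade 4 cytopenia, the more severe event also has the more permissive restart rule. The documents give no reason for any of this.

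At stake is consistent handling of an expected toxicity. Of two participants who both recover to their entry hemoglobin, one may restart SAR442720 while the other stays off it and, after 4 weeks, is considered for discontinuation of both drugs. The SAP tabulates TEAEs leading to SAR442720 dose modification and discontinuation (Section 4.3, Table 5) and SAR442720 relative dose intensity (Section 4.7.1.2). Those outputs would then partly reflect how a site read the tables.

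**Working it through.** **1. The release rules side by side (Protocol, Appendix 9).**

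| Rule | Drug | Grade needed | Baseline accepted | Restart level |
|---|---|---|---|---|
| Table 26, Grade 3 | SAR442720 | 1 or lower | yes | not stated |
| Table 27, Grade 3 anemia | SAR442720 | below 1 | **no** | one lower |
| Table 27, Grade 3 anemia | adagrasib | 1 or lower | yes | same |
| Table 27, Grade 3 neutropenia, thrombocytopenia | both | below 1 | yes | SAR442720 one lower |
| Table 27, Grade 4 cytopenias | both | below 1 | yes | SAR442720 and adagrasib one lower |
| Table 27, uncomplicated thrombocytopenia, Grade 3 to 4 | both | 1 or lower | no | same |

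**2. Who meets the SAR442720 anemia rule by returning to baseline alone.**

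| Entry status | Below Grade 1 (Table 27 as written) | Grade 1 or lower, no baseline option | Grade 1 or lower, or baseline (Table 26) |
|---|---|---|---|
| Normal | yes | yes | yes |
| Grade 1 | no | yes | yes |
| Grade 2 | no | no | yes |

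So if the sign in Table 27 was meant to include Grade 1, the gap narrows to those who entered at Grade 2 but does not close. Whether E 23 admits Grade 2 depends on CTCAE hemoglobin cut-offs that the documents do not give. I treat it as an assumption.

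**3. Scale.** Table 11's figures reproduce: any-grade anemia 42/113 = 37.2%; Grade 3 or higher 19/113 = 16.8%. Carried over to a part with 40 participants:

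40 × 19/113 = 6.7, or about 7 in Part-2 and about 7 in Part-3B.

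This counts everyone with Grade 3 or higher anemia. Those affected are the subset who are held, entered anemic, and are not lifted above entry by transfusion. It is therefore an upper bound, and it assumes that the monotherapy rate applies to these combinations and populations.

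**4. How often the problem case arises.** The amendment history (Appendix 15, amendment 02) carries earlier monotherapy data, n = 82, used here only as data. It lists shifts to Grade 3 hemoglobin as 3 from Grade 1, 2 from normal, and: "5 (6.1%) participants had a hemoglobin shift from Grade 2 to Grade 3".

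- Total: 3 + 5 + 2 = 10.
- From an anemic baseline: 3 + 5 = 8 of 10 = 80% (exact 95% CI 44% to 97%).
- From Grade 2: 5 of 10, the relevant count if Grade 1 was meant to suffice.

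The same text reports Grade 3 anemia events in 13 participants, so the 10 laboratory shifts and the event count do not match one for one. The 80% is a rough indication that entering anemic is common among those who reach Grade 3, and no more than that.

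**The case against.** The strongest defence is that these are guidelines. The hold applies only if clinically indicated, discontinuation is only to be considered, improvement within 4 weeks is not tied to a grade, and ambiguous cases go to the Medical Monitor. Table 27 is the specific table and may be meant to prevail over Table 26. A baseline option is not universal either: the uncomplicated thrombocytopenia line has none. Inequality signs are used loosely in Table 27, where headings reading above Grade 3 cover Grade 3 instructions.

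Much of this stands, and it limits the harm. It does not tell a site whether baseline counts. Precedence of the specific table would explain a difference from Table 26, but not the difference from the adagrasib sentence in the same entry or from the Grade 4 cytopenia line. A loose sign does not account for the missing baseline words.

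The documents do not support four stronger readings that a reader might infer:

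- *Table 27 contradicts Table 11.* Table 11 addresses whether to interrupt or discontinue and sets no restart threshold. Table 27's conditional hold and its instruction to assess transfusion history are compatible with it. The fair point is that Table 11 asks investigators to weigh baseline hemoglobin, which the Table 27 release rule leaves out.
- *Participants who entered anemic can never restart.* The same entry calls for transfusion, so a value better than at entry is attainable.
- *About 7 of 40 would be affected.* That is the ceiling from step 3, at a monotherapy rate.
- *The ORR estimate is weakened.* Participants who stop SAR442720 may continue the partner drug (Section 7.1.1) and stay in the safety-population analysis (Section 9.4.1). No effect on ORR has been estimated.

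**Conclusion.** The inconsistency is real and narrow. For SAR442720 after Grade 3 anemia, Table 27 sets a release threshold below Grade 1 without a baseline option. That conflicts with Table 26, with the adagrasib sentence in the same entry, and with the Grade 3 neutropenia/thrombocytopenia and Grade 4 cytopenia lines. Participants admitted under E 23 with anemia cannot satisfy it by returning to baseline alone. The supported consequence is variation between sites in SAR442720 interruption, dose reduction and discontinuation, moderated by the tables' status as guidelines.

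The size rests on two assumptions: that the monotherapy rate of 16.8% carries over, which bounds the affected at about 7 of 40 in each expansion part, and that the baseline mix resembles the earlier monotherapy data. Reading Grade 4 anemia as a Grade 4 cytopenia is a literal reading of Table 27, which has no separate Grade 4 anemia line.

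**What to change.** Reconcile the Grade 3 anemia entry of Table 27 with Table 26 and with the related Table 27 lines. State one release threshold for SAR442720, and say explicitly whether return to baseline satisfies it, given that E 23 admits participants who are already anemic. If a stricter rule than for Grade 4 cytopenias is intended, say so and give the reason. Table 11 needs at most a cross-reference. The choice of threshold is the sponsor's. The cost is one line of protocol text at the next amendment, with no change to sample size or planned analyses.
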